5.9.2. Analysis of NAb Data

The absolute occurrence (n) and percent of subjects (%) with NAb status in the NAb analysis set will be provided by treatment groups.

5.10. Association of Immunogenicity with Exposure, Safety, and Efficacy

5.10.1. Immunogenicity and Exposure

Potential association between immunogenicity variables and systemic exposure to REGN10933 and REGN10987 will be explored by treatment groups. Plots of drug concentration time profiles may be provided to examine the potential impact of ADA response status, and titer on these profiles.

5.10.2. Immunogenicity and Safety and Efficacy

Potential association between immunogenicity variables and safety may be explored with a primary focus on the following safety events during the TEAE period:

- Infusion reactions
- Hypersensitivity (SMQ: Hypersensitivity [Narrow])
- Anaphylaxis (SMQ: Anaphylaxis [Narrow])

Potential association between immunogenicity variables and efficacy endpoints may be explored (e.g. scatter plot or spaghetti plot).

The safety and efficacy analyses mentioned above will be conducted using the following categories:

- ADA positive subjects: Subjects with treatment-emergent or treatment-boosted response.
- Maximum post-baseline titer.
- NAb positive

6. DATA CONVENTIONS

The following analysis conventions will be used in the statistical analysis.

6.1. Definition of Baseline for Efficacy/Safety Variables

Definitions of baseline for efficacy variables are defined in Section 4.5.1.1. Baseline viral load value will be the latest available valid measurement before the administration of study drug or the measurement taken within 2 hours after the administration of study drug if the pre-treatment measurement is missing.

For safety variables, baseline will be the latest available valid measurement taken prior to the administration of study drug.

6.2. Data Handling Convention for Efficacy Variables

The virologic endpoint analysis will be based on the observed data with no imputation for missing data except as defined in Section 4.5.1.1 for viral load values that are below lower limit of detection (<LLOD), below lower limit of quantification (<LLOQ) or above upper limit of quantification (>ULOQ) of the assay.

In the analysis for the clinical endpoints based on proportions of patients with the event, the missing data will be considered as non-events.

6.3. Data Handling Convention for Missing Data

For categorical variables, patients with missing data will be included in calculation of percentages. Number of patients with missing data will be presented

Handling of Medications with Missing/Partial Dates

To determine whether a medication is prior or concomitant medication, the missing medication start date is estimated as early as possible up to first dose date, and the missing medication end date is estimated as late as possible up to day 29. If the medication start date is missing, the onset day will not be imputed in medication listings.

Handling of AE Missing and Partial Start Dates

Every effort will be made to collect the start dates of all AEs. However, in the case the start date of an AE is incomplete or missing, it will be assumed to have occurred on or after the first dose of study medication, except if an incomplete date (e.g., month and year) clearly indicates that the event started prior to treatment. If the partial date indicates the same month or year of the first dose of study medication date, then the start date of the first dose will be imputed, otherwise, the missing day or month by the first day or the first month will be imputed.

Handling of Adverse events Severity and Relatedness

If the intensity of an SAE or AESI is missing, it will be classified as “Grade 3” in the frequency tables by CTC grade of SAE or AESIs. If the assessment of relationship of the investigational product is missing, it will be classified as related to the investigational product.

Date of infusion

Date of infusion is the non-missing administration date filled in the Drug Administration-Infusion CRF. If the first dose of study drug administration date is missing (even after site is queried), then the dosing date will be imputed with the randomization date. If any subsequent study drug administration date is missing, the date of dispensation of study drug from IRT will be used.

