4.2. Secondary Endpoints

Pooled Phase 3 (Cohort 1) and Phase 2 (Cohort 1A)

Clinical

- Proportion of patients who went on mechanical ventilation by day 29
- Proportion of patients who died from day 6 to day 29 and from day 1 to day 29
- Proportion of patients who were discharged by day 29
- Proportion of patients who died or were readmitted to hospital over time
Note: Readmission to hospital will be based on investigator report.
- Cumulative incidence of death over time (ie, overall survival)
- Cumulative incidence of mechanical ventilation over time
- Cumulative incidence of death or mechanical ventilation over time
- Time to discharge

Safety and Tolerability

- Proportion of patients with treatment-emergent SAEs through end of study
- Proportion of patients with infusion-related reactions (grade ≥ 2) through day 4
- Proportion of patients with hypersensitivity reactions (grade ≥ 2) through day 29

Phase 1/2 (Cohort 1)***Clinical Efficacy***

The key secondary endpoint is death or mechanical ventilation.

Other secondary endpoints include:

Virologic Efficacy

- Time-weighted average change from baseline in viral load (\log_{10} copies/mL) from day 1 to day 7, as measured by quantitative reverse transcription polymerase chain reaction (RT-qPCR) in nasopharyngeal (NP) swab samples

Note: Time-weighted average of change from baseline in viral load from day 1 to day 7 will be calculated for each patient using the trapezoidal rule as the area under the curve for change from baseline at each time point divided by the time interval for the observation period.

- Time-weighted average change from baseline in viral load (\log_{10} copies/mL) from day 1 to day 11, as measured by RT-qPCR in NP swab samples
- Time-weighted average change from baseline in viral load (\log_{10} copies/mL) from day 1 to each post-baseline timepoint until day 29, as measured by RT-qPCR in NP swab samples
- Change from baseline in viral load at each post-baseline timepoint through day 29, as measured by RT-qPCR in NP swab samples
- Time to sustained negative RT-qPCR (negative RT-qPCR with no subsequent) positive

Clinical Efficacy

- All-cause death
- Mechanical ventilation
- Proportion of patients who died or went on mechanical ventilation by day 29
- Proportion of patients who died by day 29
- Proportion of patients who went on mechanical ventilation by day 29
- Time to discharge

PK/ADA

- Concentrations of REGN10987 and REGN10933 in serum and corresponding PK parameters

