4.6. Safety Variables

4.6.1. Adverse Events and Serious Adverse Events

Treatment-emergent adverse events (AEs) (grade 3 or 4; for phase 1 only), treatment-emergent serious adverse events (SAEs) and treatment-emergent adverse events of special interest (AESIs) will be collected according to the Schedule of Events (Appendix 10.1 and Appendix 10.2). All adverse events are to be coded using the Medical Dictionary for Regulatory Activities (MedDRA).

Treatment-emergent adverse events are defined as those that are not present at baseline or represent the exacerbation of a pre-existing condition.

Infusion-related reactions are defined as any relevant adverse event that occurs during the infusion or up to day 4.

Hypersensitivity reactions are defined as any relevant adverse event that occurs during the infusion or up to study day 29.

The severity of adverse events (including test findings classified as adverse events) will be graded using the current version of the NCI-CTCAE v5.0 (Division of Cancer Treatment and Diagnosis [DCTD], 2020).

Treatment-emergent AEs, treatment-emergent SAEs, or treatment-emergent AESIs not listed in the NCI-CTCAE will be graded according to the scale in [Table 8](#).

Table 8: NCI-CTCAE Severity Grading System for Adverse Events

Grade	Severity	Description
1	Mild	Asymptomatic or mild symptoms; clinical or diagnostic observations only; intervention not indicated
2	Moderate	Minimal, local, or noninvasive intervention indicated; limiting age appropriate instrumental activities of daily living (ADL)*
3	Severe	Severe or medically significant but not immediately life threatening; hospitalization or prolongation of hospitalization indicated; disabling; limiting self-care ADL†
4	Life-threatening	Life threatening consequences; urgent intervention indicated
5	Death	Death related to adverse events

*Instrumental ADL refers to preparing meals, shopping for groceries or clothes, using the telephone, managing money, etc.

† Self-care ADL refers to bathing, dressing, and undressing, feeding self, using the toilet, taking medications, and not bedridden.

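### Read as written, the partial-date rule for adverse events sets an onset in a known later month of the dosing year to day 1, and the missing-grade rule makes no exception for fatal events (minor)

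*SAP*

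**What the plan says.** SAP 6.3 first assumes that an adverse event with an incomplete or missing start date began on or after first dose, "except if an incomplete date (e.g., month and year) clearly indicates that the event started prior to treatment". It then gives the imputation. The trigger is worded "If the partial date indicates the same month or year of the first dose of study medication date". When it is met, the consequence, together with the fallback for all remaining dates, is "then the start date of the first dose will be imputed, otherwise, the missing day or month by the first day or the first month". The first-of-month fallback therefore applies only when neither month nor year matches dosing. The one exception protects events clearly before treatment. There is no counterpart for events clearly in a later month.

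Onset day enters two safety definitions in SAP 4.6.1: "Infusion-related reactions are defined as any relevant adverse event that occurs during the infusion or up to day 4" and "Hypersensitivity reactions are defined as any relevant adverse event that occurs during the infusion or up to study day 29". Protocol 4.2 makes both into endpoints: "Proportion of patients with infusion-related reactions (grade ≥ 2) through day 4" and "Proportion of patients with hypersensitivity reactions (grade ≥ 2) through day 29".

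On grading, SAP 6.3 says "If the intensity of an SAE or AESI is missing, it will be classified as" Grade 3 in the frequency tables by grade, with no condition on outcome. SAP Table 8 defines Grade 5 as death.

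**The concern.** An imputation rule should fill in what is missing and leave what is known alone. Here a recorded month can be overwritten by an earlier date that the record itself rules out. Day 1 lies inside both the day 4 and the day 29 windows, so a late reaction with a missing day would count as an early one. Equivalent records are also treated differently depending on whether New Year falls between dose and event.

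The grade rule has a similar fault. A fatal SAE with missing intensity would appear as Grade 3 in the by-grade table and as fatal in the overview of SAP 5.7.1.

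**Working it through.** The plan gives no figure to reproduce, so the check applies the rule to dates.

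**Inputs.** The rule and its exception are in SAP 6.3 and the windows in SAP 4.6.1. Phase 2/3 follow-up runs to day 57 (SAP 2.4.1). Phase 3 cohort 1 enrolled after 01 December 2020, and enrollment was terminated on 09 April 2021 (SAP 1.1). Study day = event date − first-dose date + 1.

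**Single cases**, month and year known, day missing:

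| First dose | Recorded onset | Earliest possible day | Rule as written | Month and year compared together |
|---|---|---|---|---|
| 25 Feb 2021 | Mar 2021 | 5 | 1 | 5 |
| 25 Jan 2021 | Feb 2021 | 8 | 1 | 8 |
| 05 Jan 2021 | Feb 2021 | 28 | 1 | 28 |
| 20 Jan 2021 | Mar 2021 | 41 | 1 | 41 |
| 28 Dec 2020 | Jan 2021 | 5 | 5 | 5 |
| 20 Dec 2020 | Jan 2021 | 13 | 13 | 13 |

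For example, 25 February is day 1, 28 February is day 4 and 01 March is day 5. The two December rows escape only because the year differs and neither part matches. A patient dosed on 09 April 2021 reaches day 57 on 04 June 2021, so no 2021 dose escapes in this way.

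**All date combinations.** Dosing dates from 02 December 2020 to 09 April 2021 (129) times onset days 1 to 57 give 129 × 57 = 7353 combinations. Of these, 5256 have onset in a later calendar month than the dose.

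- Under the rule as written, 4011 of the 5256 (76%) go to day 1. The other 5256 − 4011 = 1245 are December doses with onset in the new year, which go to the first of the onset month.
- True onset after day 4 (5232 combinations): 4080 (78%) land in days 1 to 4 under the rule as written, against 336 (6%) when month and year are compared together.
- True onset after day 29 (3604 combinations): 3224 (89%) land in days 1 to 29, against 1915 (53%).

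These are counts of dates, each weighted equally by assumption. They are not patients or expected events. They describe what the rule does to a later-month onset with the day missing, not how often that occurs.

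**Grade rule.** Protocol 10.1.1 requires the cause of every death to be reported as an SAE, so every fatal case falls within the scope of the missing-intensity rule. Grade 3 then disagrees with SAP Table 8 for any such case with no grade entered.

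**The case against.** The best defense is that the sentence means 'respectively': when the day is missing compare the month, and when the month is also missing compare the year. Its second half uses 'or' in that sense. The literal reading also sits badly with the sentence before it: a dose on 10 February 2021 with onset 'Jan 2021' would match on year and receive the dosing date, although the exception says such an event stays pre-treatment. This intent is plausible, but it needs words the SAP does not contain, and two programmers could derive different datasets from the same text.

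The objections on reach largely stand.

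- An imputed date does not make an event an AESI. Under SAP 4.6.2, AESIs are selected from the Adverse Events CRF, and the windows cover relevant events only. Protocol 3.2.1.5 describes AESI collection through day 29, and Protocol 10.1.3 requires reporting within 24 hours. A late event would have to be reported as a reaction despite lying outside its window, and with its day missing.
- A reader might infer that SAE results are distorted. They are not: the SAE endpoint runs through end of study, and SAP 5.7.1 lists no summary by onset day.
- A reader might infer that every incomplete 2021 date is mishandled. Dates in the dosing month receive the first-dose date under either reading, and doing the same for year-only dates is an ordinary conservative choice.
- A reader might infer that the infusion-reaction rate would shift materially. The documents give no count of partial dates. The rate of under 0.3% in Protocol 3.3.1 is an upper bound from an outpatient trial and cannot serve as an expected count here.
- The rule is the same in every arm and leans toward associating events with dosing, so the text gives no ground for claiming bias between arms.

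On grading, Protocol 10.1.2 requires severity for every SAE, and fatal events have their own overview row. Deaths would not be lost; only the by-grade table would be wrong.

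**Conclusion.** The point holds as a minor one. Read as written, the rule replaces a known later month in the dosing year with day 1, which contradicts recorded information. It can change onset day for the two windowed safety endpoints, but only for events reported as those reactions with the day missing. SAE counts are unaffected. The number of such dates is unknown and the practical effect is probably small.

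Correcting the rule helps mainly at day 4. At day 29 it helps only in part, because the first of a month can precede the true onset by several weeks. The percentages rest on equally likely dosing dates and onset days and are illustrative.

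The grade rule is a separate minor inconsistency with SAP Table 8. It affects only fatal events with no grade recorded, a number the documents also do not give.

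**What to change.** Replace the date sentence in SAP 6.3 with:

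> If month and year are both known and equal those of the first dose, or only the year is known and equals the year of the first dose, impute the first-dose date; otherwise impute the first day of the known month, or 01 January of the known year. Dates clearly before treatment stay pre-treatment.

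Replace the missing-intensity rule with:

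> If the intensity of an SAE or AESI is missing, classify it as Grade 5 if the outcome is fatal, otherwise Grade 3.

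The first change keeps the conservative default wherever the record is truly ambiguous and preserves any month that was recorded. The second brings the by-grade table into line with Table 8 and with the separate count of fatal events. The cost is two edits to the SAP and a few lines of derivation code before database lock. No new data are needed.

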6.4. Visit Windows

Data analyzed by-visit-analysis will be summarized by the study scheduled visits described in the “Schedule of Events” Appendices 10.1 and 10.2. The analysis visit windows will be exhaustive so that all available values obtained from unscheduled visits, early termination visit (ETV) and end of treatment (EOT)/end of study (EOS) have the potential to be summarized. No analysis visit windows will be applied for the study scheduled visits and discharge visit.

The following analysis visit windows will be used to map the unscheduled visits, ETV and EOT visits for Nasopharyngeal swab, saliva and nasal samples for SARS-CoV-2 RT-qPCR, based on the study day during the study:

Table 10: Time Window for Summary of Swab Samples for SARS-CoV-RT-qPCR

Visit Label	Targeted Study Day	Analysis Window in Study Day
Baseline	1	≤ 1
Day 3	3	[2, 3]
Day 5	5	[4, 5]
Day 7	7	[6, 7]
Day 9	9	[8, 9]
Day 11	11	[10, 11]
Day 13	13	[12, 13]
Day 15	15	[14, 18]
Day 22	22	[19, 25]
Day 29	29	[26, 32]

The following analysis visit windows will be used to map the unscheduled visits for laboratory variables, based on the study day during the double blind period:

Table 11: Time Window for Summary of Laboratory Variables and Biomarkers

Visit Label	Targeted Study Day	Analysis Window in Study Day
Baseline	1	≤ 1
Day 7	7	For phase 1 [2, 18] For phase 2/3 [2, 11]
Day 15	15	For phase 2/3 only [12, 22]
Day 29	29	For phase 1 [19, 32] For phase 2/3 [23, 32]
Day 57	57	For phase 1 only [33, 71]

6.5. Pooling of Centers for Statistical Analyses

Data from countries (US and non-US) will be pooled in the phase 1/2/3 analysis.

7. INTERIM ANALYSIS

This SAP is for the final analysis of the study. No interim analyses were planned or conducted for Phase 3 portion of the study.

8. SOFTWARE

All analyses will be done using SAS Version 9.4 or above.

10. APPENDIX

10.1. Schedule of Events for Phase 1 (Cohort 1)

Day	Screening/Baseline ¹				Hospitalization/Post-Discharge Period ²																	EOS						
	-1 to 1				Discharge Before Day 29	2	3	4	5	6	7	8	9	10	11	12	13	14	15	16, 17, 18, 19, 20, 21	22	23, 24, 25, 26, 27, 28	29	57	85	113	141	169
	Screen	Pre-Dose	Dose	Post-Dose																								
Week Number	1				1	1	1	1	1	1	1	2	2	2	2	2	2	2	3	3	4	4	5	9	13	17	21	25
Visit Number	1				2	3	4	5	6	7	8	9	10	11	12	13	14	15	16-21	22	23-28	29	30	31	32	33	34	
Window (Days)					±1						±1	±1	±1	±1	±1	±1	±1	±1	±3		±3	±7	±7	±7	±7	±7	±7	
Screening/Baseline Only																												
Informed consent	X																											
PGx sub-study consent (optional) ³	X																											
Inclusion/exclusion	X																											
Antigen or molecular diagnostic test for SARS-CoV-2 (local) ⁴	X																											
Demographics	X																											
Medical history ⁵	X																											
Weight and height	X																											
Randomization		X																										
Treatment																												
Study drug administration			X																									
Safety Assessments																												
Vital signs ⁶	X	X	X																									
Treatment-emergent grade ≥ 2 infusion-related reactions ^{7,8}				← Continuous monitoring →																								
Treatment-emergent grade ≥ 2 hypersensitivity reactions ^{7,8}																				← Continuous monitoring →								
Treatment-emergent SAEs ^{7,8}																				← Continuous monitoring →								
Grade 3 or 4 TEAEs ^{7,8}																				← Continuous monitoring →								
Targeted concomitant medications ^{8,9}	X	X																		← Continuous monitoring →								
Post-discharge phone follow-up ⁸																				X					X			X

Day	Screening/Baseline ¹				Hospitalization/Post-Discharge Period ²																		EOS					
	-1 to 1				Discharge Before Day 29	2	3	4	5	6	7	8	9	10	11	12	13	14	15	16, 17, 18, 19, 20, 21	22	23, 24, 25, 26, 27, 28	29	57	85	113	141	169
	Screen	Pre-Dose	Dose	Post-Dose																								
Week Number	1				1	1	1	1	1	1	1	2	2	2	2	2	2	2	3	3	4	4	5	9	13	17	21	25
Visit Number	1				2	3	4	5	6	7	8	9	10	11	12	13	14	15	16-21	22	23-28	29	30	31	32	33	34	
Window (Days)					±1							±1	±1	±1	±1	±1	±1	±1	±1	±3		±3	±7	±7	±7	±7	±7	
Pregnancy test (WOCBP) ¹⁰	X																											X
Local Laboratory Testing																												
Hematology (including differential) ¹¹	X				X							X												X	X			
Blood chemistry (including AST, ALT, CRP, ferritin, LDH) ¹¹	X				X							X												X	X			
Coagulation tests (D-dimer, PT/INR, aPTT) ¹¹	X				X							X												X	X			
Efficacy Assessments (Virologic)																												
Saliva for SARS-CoV-2 RT-qPCR		X			X		X	X	X	X	X	X	X	X	X	X	X	X	X	X	X	X	X	X				
Nasal swab for SARS-CoV-2 RT-qPCR		X			X		X	X	X	X	X	X	X	X	X	X	X	X	X	X	X	X	X	X				
NP swab for SARS-CoV-2 RT-qPCR		X			X		X	X	X	X	X	X	X	X	X	X	X	X	X	X	X	X	X	X				
Efficacy Assessments (Clinical/Oxygen Status)																												
Oxygen delivery device status ¹²		X ¹²	X ¹²		X	X	X	X	X	X	X	X	X	X	X	X	X	X	X	X	X	X	X	X				
Vital status ¹²		X ¹²	X ¹²		X	X	X	X	X	X	X	X	X	X	X	X	X	X	X	X	X	X	X	X	X			
Hospitalization status ¹²		X ¹²	X ¹²		X	X	X	X	X	X	X	X	X	X	X	X	X	X	X	X	X	X	X	X	X			
Pharmacokinetics/Immunogenicity																												
Serum for PK ¹³		X ¹⁴		X ¹⁴	X		X	X	X	X	X	X	X	X	X	X	X	X	X	X	X	X	X	X	X	X	X	
Serum for ADA ¹⁵		X ¹⁵			X																		X	X			X	X
Pharmacodynamic/Biomarkers																												
Serum for serology		X																						X				X
Pharmacogenomics Sub-Study (Optional)																												
Blood for RNA ³		X ³																										
Blood for DNA ³		X ³																										

10.1.1. Footnotes for Schedule of Events (Phase 1)

1. Every effort should be made to perform all screening and baseline activities on the same day. Randomization within the Interactive Response Technology (IRT) system and administration of study drug should occur on the same day (day 1). All samples will be collected before study drug administration at the baseline visit except post-infusion PK samples.
2. For a given day, the visit may occur in clinic, as a home-based visit (defined as visits by home health care staff, at mobile units, and/or testing centers), or by phone. All samples will be collected as indicated whether the patient is hospitalized or has been discharged.
3. Patients must provide separate consent to collect blood samples as part of the optional pharmacogenomics (PGx) sub-study. Blood sample for RNA must be collected pre-dose on day 1. Blood sample for DNA should be collected at the screening/baseline visit but may be collected at any visit.
4. Refer to protocol Section 9.2.1.2 for diagnostic test requirements during screening.
5. Medical history should include collecting onset of pneumonia symptoms.
6. Vital signs (including respiratory rate, temperature, blood pressure, heart rate, and SpO₂) will be taken as described in protocol Section 9.2.3.1.

For patients in the phase 1 sentinel safety group only (protocol Section 3.1.1.1), vital signs will be taken once before the infusion, every 15 minutes during the infusion, every 30 minutes for the first 2 hours after the infusion is completed, and then once per hour for the following 4 hours. **For all other patients**, vital signs will be taken once before the infusion and once after the infusion is completed.

7. Only TEAEs (grade 3 or 4), treatment-emergent SAEs, and treatment-emergent AESIs will be recorded in the eCRF.
8. Patients discharged from the hospital may receive phone follow-up for TEAEs (grade 3 or 4), treatment-emergent SAEs, treatment-emergent AESIs, and/or targeted concomitant medications as indicated in the protocol table 1 (post-discharge phone follow-up). These visits may occur in addition to any in-person visit listed for the given day. Phone visits will have a window of ± 1 day.
9. Medications will be reviewed and recorded. Only the targeted medications listed in protocol Section 9.2.3.3 will be recorded in the eCRF.
10. Pregnancy testing will be performed locally in women of childbearing potential (WOCBP) only. Negative pregnancy test must be confirmed prior to study drug administration. Serum or urine pregnancy test are both acceptable. Refer to protocol Section 9.2.3.4 for more information on pregnancy testing and contraceptive measures.

11. Hematology, blood chemistry, and coagulation tests will be collected at the visits indicated and results will be entered in the eCRF. Hematology, blood chemistry, and coagulation tests must be collected prior to randomization. Testing will be performed locally, and standard-of-care labs are acceptable.
12. Clinical and oxygen status will be collected 3 times during the screening/baseline visit period: prior to randomization, just prior to dosing, and post-dose. Clinical and oxygen status will be collected and recorded in the eCRF as described in protocol Section 9.2.5.2.
13. Actual dosing time and PK sample collection times will be recorded.
14. At the baseline visit, blood samples for PK assessment will be taken predose and within 60 minutes after the end of infusion (EOI). The EOI sample should be collected from the arm contralateral to that used for IV infusion. If not medically feasible, the EOI sample can be drawn from the same arm, but not from the infusion catheter.
15. The window for predose ADA sample collection is as close to administration of study drug as is reasonable. Actual dosing times and ADA sample collection times will be recorded.

10.2. Schedule of Events for Phase 2/3 (Cohort 1A, Cohort 1, Cohort 2, Cohort 3)

Day	Screening/Baseline ¹				Hospitalization/Post-Discharge Period ²															Follow-up Period		EOS					
	-1 to 1				Discharge Before Day 29	2	3	4	5	6	7	8	9	10	11	12	13	14	15	16, 17, 18, 19, 20, 21	22	23, 24, 25, 26, 27, 28	29	36	43	50	57
	Screen	Pre-Dose	Dose	Post-Dose																							
Week Number	1				1	1	1	1	1	1	1	2	2	2	2	2	2	2	3	3	4	4	5	6	7	8	9
Visit Number	1				2	3	4	5	6	7	8	9	10	11	12	13	14	15	16-21	22	23-28	29	30	31	32	33	
Window (Days)					±1							±1	±1	±1	±1	±1	±1	±1	±1	±3		±3	±3	±3	±3	±3	
Screening/Baseline Only																											
Informed consent	X																										
PGx sub-study consent (optional) ³	X																										
Inclusion/exclusion	X																										
Antigen or molecular diagnostic test for SARS-CoV-2 (local) ⁴	X																										
Pregnancy test (WOCBP) ⁵	X																										
Demographics	X																										
Medical history ⁶	X																										
Weight and height	X																										
Randomization		X																									
Treatment																											
Study drug administration			X																								
Efficacy Assessments (Virologic)																											
NP swab for SARS-CoV-2 RT-qPCR		X				X		X	X	X	X	X	X	X	X	X	X	X	X	X	X	X	X	X	X		
Efficacy Assessments (Clinical/Oxygen Status)																											
Oxygen delivery device status ⁷		X ⁷	X ⁷		X		X	X	X	X	X	X	X	X	X	X	X	X	X	X	X	X	X	X	X		
Vital status ⁷		X ⁷	X ⁷		X		X	X	X	X	X	X	X	X	X	X	X	X	X	X	X	X	X	X	X		
Hospitalization status ⁷		X ⁷	X ⁷		X		X	X	X	X	X	X	X	X	X	X	X	X	X	X	X	X	X	X	X		
Safety Assessments																											
Vital signs ⁸			X		X																						
Treatment-emergent grade ≥2 infusion-related reactions ^{9,10}					← Continuous monitoring →																						
Treatment-emergent grade ≥2 hypersensitivity reactions ^{9,10}																											
Treatment-emergent SAEs ^{9,10}																											

Day	Screening/Baseline ¹				Hospitalization/Post-Discharge Period ²																Follow-up Period		EOS					
	-1 to 1				Discharge Before Day 29	2	3	4	5	6	7	8	9	10	11	12	13	14	15	16, 17, 18, 19, 20, 21	22	23, 24, 25, 26, 27, 28	29	36	43	50	57	
	Screen	Pre-Dose	Dose	Post-Dose																								
Week Number	1				1	1	1	1	1	1	1	2	2	2	2	2	2	2	3	3	4	4	5	6	7	8	9	
Visit Number	1				2	3	4	5	6	7	8	9	10	11	12	13	14	15	16-21	22	23-28	29	30	31	32	33		
Window (Days)					±1						±1	±1	±1	±1	±1	±1	±1	±1	±3		±3	±3	±3	±3	±3	±3		
Targeted concomitant medications ^{10,11}	X	X			← Continuous monitoring →																							
Post-discharge phone follow-up ¹⁰																									X	X	X	X
Pregnancy follow-up																												X
Local Laboratory Testing																												
Hematology (including differential) ¹²	X																											X
Blood chemistry (including AST, ALT, CRP, ferritin, LDH) ¹²	X																											X
Coagulation tests (D-dimer, PT/INR, aPTT) ¹²	X																											X
Pharmacokinetics/Immunogenicity																												
Serum for PK ¹³			X ¹⁴		X ¹⁴	X																					X	
Serum for ADA ¹⁵			X ¹⁵			X																						X
Pharmacodynamic/Biomarkers																												
Serum for serology		X																										X
Serum for cytokines and CK-MB		X																										X
Serum for research and cardiac biomarkers			X																									X
Plasma for research and cardiac biomarkers			X																									X
Plasma for hsTroponin-T		X				X																						X
Pharmacogenomics Sub-Study (Optional)																												
Blood for RNA ³			X ³																									
Blood for DNA ³			X ³																									

